4.2.2 Supply and Disposition of Treatments

Study insert will be shipped at a temperature of 2° to 8°C to the investigator as needed during the study.

4.2.3 Treatment Accountability

All study insert accountability records will be kept current.

The investigator will account for all opened and unopened packaging of study inserts. These records will contain the dates, quantity, and study medication

- Inserted in each patient,
- disposed of at the site or returned to Ocular Therapeutix

All accountability records will be made available for inspection by regulatory agency inspectors.

4.3 Concomitant Medications and Procedures

At the discretion of their physician, patients may continue to receive all medications and standard treatments administered for other conditions.

5. STUDY SCHEDULE OF EVENTS AND VISIT DESCRIPTIONS

5.1 Schedule of Events

Study assessments and procedures are presented by visit in Table 1.

Table 1 Schedule of Events

Study Procedure	Screening/ Baseline	Insertion Visit Day 0	Day 7	Day 30	Day 90	Early Termin ation
Visit	VISIT 1	VISIT 2	VISIT 3	VISIT 4	VISIT 5	
Windows for Visits	(Day -30 to - 1)		(+/- 2 days)	(+/- 3 days)	(+/- 3 days)	
Inclusion/Exclusion	X					
Informed Consent	X					
Demographics	X					
Medical History and Concurrent Illnesses	X					
Concomitant Medications	X	X	X	X	X	X
Uncorrected Distance VA testing (ETDRS at 4m)	X	X	X	X	X	X
MR/BCVA (ETDRS at 4m)	X	X	X	X	X	X
Ophthalmic Examination (with or without dilation)	X	X	X	X	X	X
QOL Assessment (OSDI questionnaire)	X	X	X	X	X	X
Osmolarity (Needs to be done prior to any drop instillation)	X	X	X	X	X	X
MMP9 (Needs to be done prior to any drop instillation)	X	X	X	X	X	X
Grading of itching (Scale 0-4)	X	X	X	X	X	X
Papillae conjunctivitis assessment (Efron Scale)	X	X	X	X	X	X
Conjunctival Injection (Scale 0- 4)	X	X	X	X	X	X
Corneal staining (NEI Fluorescein Scale)	X	X	X	X	X	X
TBUT	X	X	X	X	X	X
Intraocular Pressure (IOP)	X	X	X	X	X	X
Intracanalicular dexamethasone insert*		X				
Insert Visualization		X	X	X	X	X
Subject reported AEs after insertion		X	X	X	X	X
Physician ease of insertion as measured on a 0-10 point scale		X				

COMTOL					X	X
--------	--	--	--	--	---	---

5.2 Study Visit Descriptions

5.2.1 Study Procedures

Screening/Baseline (Visit 1)

After the patient has provided informed consent, the following information will be collected:

- Inclusion/Exclusion
- Demographics
- Medical History and Concurrent Illnesses
- Concomitant Medications
- Uncorrected and best-corrected visual acuity with manifest refraction as measured by ETDRS chart at 4 meters
- Ophthalmic Examination (with or without dilation)
- QOL assessment as measured by OSDI questionnaire
- Osmolarity (Needs to be done prior to any drop instillation)
- MMP9 (Needs to be done prior to any drop instillation)
- Grading of itching (scale 0-4)
- Papillae conjunctivitis assessment (Efron Scale)
- Conjunctival Injection
- Corneal Staining
- TBUT
- Intraocular Pressure

Insertion Visit/Day 0 (Visit 2)

- Concomitant Medications
- Uncorrected and best-corrected visual acuity with manifest refraction as measured by ETDRS chart at 4 meters
- Ophthalmic Examination (with or without dilation)
- QOL assessment as measured by OSDI questionnaire
- Osmolarity (Needs to be done prior to any drop instillation)
- MMP9 (Needs to be done prior to any drop instillation)
- Grading of itching (scale 0-4)
- Papillae conjunctivitis assessment (Efron Scale)
- Conjunctival Injection
- Corneal Staining
- TBUT
- Intraocular Pressure
- Insertion of Dextenza (intraocular dexamethasone insert)
- Insert Visualization
- Subject reported AEs after insertion
- Physician ease of insertion grading

Day 7 (Visit 3)

- Concomitant Medications

- Uncorrected and best-corrected visual acuity with manifest refraction as measured by ETDRS chart at 4 meters
- Ophthalmic Examination (with or without dilation)
- QOL assessment as measured by OSDI questionnaire
- Osmolarity (Needs to be done prior to any drop instillation)
- MMP9 (Needs to be done prior to any drop instillation)
- Grading of itching (scale 0-4)
- Papillae conjunctivitis assessment (Efron Scale)
- Conjunctival Injection
- Corneal Staining
- TBUT
- Intraocular Pressure
- Insert Visualization
- Subject reported AEs after insertion

Day 30 (Visit 4)

- Concomitant Medications
- Uncorrected and best-corrected visual acuity with manifest refraction as measured by ETDRS chart at 4 meters
- Ophthalmic Examination (with or without dilation)
- QOL assessment as measured by OSDI questionnaire
- Osmolarity (Needs to be done prior to any drop instillation)
- MMP9 (Needs to be done prior to any drop instillation)
- Grading of itching (scale 0-4)
- Papillae conjunctivitis assessment (Efron Scale)
- Conjunctival Injection
- Corneal Staining
- TBUT
- Intraocular Pressure
- Insert Visualization
- Subject reported AEs after insertion

Day 90 (Visit 5) or Early Termination

- Concomitant Medications
- Uncorrected and best-corrected visual acuity with manifest refraction as measured by ETDRS chart at 4 meters
- Ophthalmic Examination (with or without dilation)
- QOL assessment as measured by OSDI questionnaire
- Osmolarity (Needs to be done prior to any drop instillation)
- MMP9 (Needs to be done prior to any drop instillation)
- Grading of itching (scale 0-4)
- Papillae conjunctivitis assessment (Efron Scale)
- Conjunctival Injection
- Corneal Staining

- TBUT
- Intraocular Pressure
- Insert Visualization
- Subject reported AEs after insertion
- COMTOL

5.2.2 Unscheduled Visits

All attempts should be made to keep patients on the study schedule. Unscheduled visits may be necessary to repeat testing following abnormal laboratory results, for follow-up of AEs, or for any other reason, as warranted.

5.2.3 Adverse Event Information Collection

The investigator (or designee) will record all AEs that occur during the study. The definition of an AE and SAE, and information on the determination of severity and relationship to treatment are provided in Section 6.

5.3 Rescue Criteria

Patients can be rescued at any time at the discretion of the investigator with loteprednol etabonate ophthalmic gel 0.38%. Rescue criteria includes:

- A score greater than or equal to 2+ in one or more of the following categories:
 - Itching
 - Papillae
 - Injection
 - Staining

6. SAFETY DEFINITIONS, REPORTING, AND MONITORING

6.1 Definitions

6.1.1 Adverse Event

An AE is any untoward medical occurrence in a patient administered a study drug which may or may not have a causal relationship with the study drug. Therefore, an AE is any unfavorable and unintended sign (including abnormal laboratory finding), symptom, or disease which is temporally associated with the use of a study drug, whether or not considered related to the study drug.

An AE also includes any worsening (i.e. any clinically significant change in frequency and/or intensity) of a pre-existing condition that is temporally associated with the use of the study drug.

6.1.2 Serious Adverse Event

A SAE is any untoward medical occurrence that at any dose:

- Results in **death** – includes all deaths, even those that appear to be completely unrelated to study drug (e.g. a car accident in which a patient is a passenger).
- Is **life-threatening** – in the view of the investigator, the patient is at immediate risk of death at the time of the event. This does not include an AE that had it occurred in a more severe form, might have caused death.
- Requires in-patient **hospitalization** or prolongation of existing hospitalization. In-patient hospitalization is defined as admission to a hospital or an emergency room for longer than 24 hours. Prolongation of existing hospitalization is defined as a hospital stay that is longer than was originally anticipated for the event, or is prolonged due to the development of a new AE as determined by the investigator or treating physician.
- Results in persistent or significant **disability/incapacity** (substantial disruption of one's ability to conduct normal life functions).
- Is a **congenital anomaly/birth defect**
- Is an **important medical event** – Important medical events may not be immediately life-threatening or result in death or hospitalization, but may jeopardize the patient or may require intervention to prevent 1 of the other serious outcomes listed above (e.g., intensive treatment in an emergency room or at home for allergic bronchospasm; blood dyscrasias or convulsions that do not result in hospitalization; or development of drug dependency or drug abuse). Any malignancy (other than basal cell skin cancers) would be considered a medically important event.

6.2 Recording and Reporting Adverse Events

All AEs and SAEs will be recorded only if they are medically relevant.

All SAEs, regardless of assessment of causal relationship to study insert will be reported to Ocular Therapeutix.

To report an SAE, Ocular Therapeutix will be contacted at the following:

[contact]

SAE [contact]

The investigator will promptly report to the IRB all unanticipated problems involving risks to patients. This includes death from any cause and all SAEs related to the use of the study insert. All SAEs will be reported to the IRB, regardless of assessed causality.

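### Section 5.2.3 has every adverse event recorded; Section 6.2 records only those judged medically relevant, a term the protocol never defines

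*Combined protocol and SAP*

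**What the plan says.** Section 5.2.3 (Adverse Event Information Collection) sets an unrestricted rule: "The investigator (or designee) will record all AEs that occur during the study". It then refers the reader onward, saying that the AE and SAE definitions and "information on the determination of severity and relationship to treatment are provided in Section 6".

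Section 6.1.1 defines the event broadly: "An AE is any untoward medical occurrence in a patient administered a study drug", whether or not it is causally related.

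Section 6.2 (Recording and Reporting Adverse Events) sets a restricted rule: "All AEs and SAEs will be recorded only if they are medically relevant". The same section sets two reporting duties for serious events without that restriction: "All SAEs, regardless of assessment of causal relationship to study insert will be reported to Ocular Therapeutix", and "All SAEs will be reported to the IRB, regardless of assessed causality".

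The schedule of events (Table 1) and the visit descriptions in Section 5.2.1 list patient-reported AEs after insertion at Visits 2 to 5, and Table 1 also lists them at early termination. Neither place mentions relevance.

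**The concern.** An investigator who follows Section 5.2.3 writes down every event. One who follows Section 6.2 first decides whether the event is medically relevant and, if not, leaves it out. Nothing in the protocol says how to make that decision or which section takes precedence.

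This matters because safety is part of what the trial sets out to show. The title names the safety of the insert compared with loteprednol, and Section 3.1 gives safety as an aim. Section 3.1 also describes an open-label study, so the person judging relevance knows which eye has the insert and which has the gel. An undefined, unblinded judgement about what enters the record could thin the AE data, and could do so unequally between treatments. An event that was never recorded may not be recoverable at analysis.

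**Working it through.** No plan figure needs reproducing; the check is mainly a comparison of text.

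**1. Do the two rules conflict?** Take an event that meets the Section 6.1.1 definition.

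| Judgement on the event | Section 5.2.3 | Section 6.2 | Both satisfied? |
|---|---|---|---|
| Medically relevant | record | record | yes |
| Not medically relevant | record | do not record | no |

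The conflict is confined to the second row. If every event is judged relevant, it never arises.

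**2. Does any other wording define the term?** It occurs once, in Section 6.2. There are two near neighbours:

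- Section 6.1.2: "Any malignancy (other than basal cell skin cancers) would be considered a medically important event". This is a test of seriousness. Used as the recording filter, it would exclude non-serious events, which Section 5.2.3 does not allow.
- Section 6.1.1: "any clinically significant change in frequency and/or intensity". This qualifies only the worsening of a pre-existing condition. It is no threshold for new events.

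**3. Does Section 5.2.3 make room for the filter by referring to Section 6?** No. It refers there for definitions, severity and relationship, not for a limit on which events are recorded.

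**4. Which events are exposed?** The filter sentence names SAEs as well as AEs. Read literally, an SAE could be reportable to the manufacturer and the IRB yet not recorded, so Section 6.2 is also at odds with itself. In practice the reporting duties protect SAEs. Non-serious events have no such protection.

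**5. Scale.** The documents give no AE rate, so the number of omitted events cannot be calculated. What can be calculated is the weight of one eye. The synopsis gives 20 patients (40 eyes), one eye per treatment in each patient:

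- eyes per treatment = 40 / 2 = 20
- one eye = 1 / 20 = 0.05, or 5 percentage points of by-eye AE incidence

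This assumes full enrolment and a by-eye AE table. Such a table is an inference from the fellow-eye design; the protocol does not plan one. Systemic events could not be assigned to either eye.

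**6. Secondary check: severity and relationship.** Section 5.2.3 places two items in Section 6, the determination of severity and of relationship to treatment. Sections 6.1.1, 6.1.2 and 6.2 contain no rule for either. The table of contents lists no Section 6 subsection after 6.2, so no further subsection appears to have been lost.

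**The case against.** The strongest reply accepts the conflict and disputes its weight.

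- **The sentence looks stray.** Patient-reported AEs are scheduled at every visit from insertion onward with no relevance condition, so staff may collect everything regardless. This lowers the practical risk but does not settle the rule: listing a procedure does not say which of its findings must be recorded.
- **AE incidence is not a listed endpoint.** IOP spikes are the only endpoint that is explicitly an adverse outcome, and they come from scheduled measurements. Itching, papillae, injection, staining, visual acuity, TBUT and IOP are measured at every visit, so much ocular change is captured anyway. This stands. The exposure is mainly to non-serious events outside those measures, such as insert discomfort, lid symptoms or systemic complaints.
- **The 5-point figure is only the resolution of a 20-eye proportion.** Correct. It says nothing about how often the filter would operate and is given only for scale.
- **Deletion is not the only remedy.** Defining the term and narrowing Section 5.2.3 to match would also remove the contradiction. It would, however, leave unblinded staff filtering events, and it fits less well with the broad definition in Section 6.1.1 and the unfiltered schedule.
- **The severity and relationship gap is a separate matter.** Also correct. It adds nothing to the main point and is kept secondary.

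**Conclusion.** The concern holds. Sections 5.2.3 and 6.2 give incompatible instructions for any AE judged not medically relevant, the term is undefined, and no precedence rule exists. Both sentences are complete in the text, so neither redaction nor PDF conversion explains the conflict. Confidence in the contradiction is high.

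Its effect on results is unknown. The wording creates a risk of incomplete and possibly treatment-dependent recording of non-serious AEs; no lost event and no direction of bias is shown. The efficacy endpoints do not depend on the AE record. The point should be fixed because safety is a stated aim and the correction is nearly free, but it does not threaten the primary analysis.

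**What to change.** In Section 6.2, delete the limiting clause so that the sentence simply says all AEs and SAEs will be recorded. That matches Section 5.2.3 and removes the tension with the SAE reporting duties. Make the change before data collection.

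Secondarily, either add to Section 6 the rules for grading severity and judging relationship to treatment, or remove the cross-reference in Section 5.2.3.

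Optionally, if the case report form does not already do so, record for each AE whether it concerns the insert eye, the loteprednol eye, both eyes or is systemic. The form is not in the documents, so this is a suggestion rather than a correction.

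The cost is one deleted clause, either two short rules or one removed cross-reference, and at most one form field. Staff will have a few more AE lines to record. No patients, visits or procedures are added.

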7. ETHICAL AND REGULATORY CONSIDERATIONS

7.1 Good Clinical Practice Statement

It is the responsibility of the investigator(s) to ensure that this clinical study will be conducted in accordance with the ethical principles that have their origin in the Declaration of Helsinki, and that are consistent with the ICH guidelines for Good Clinical Practice (GCP) and applicable regulatory requirements.

7.2 Informed Consent

The principles of informed consent are described in ICH Guidelines for GCP.

Ocular Therapeutix will have the right to review and comment on the informed consent form.

It is the responsibility of the investigator or designee (if acceptable by local regulations) to obtain written informed consent from each patient prior to his/her participation in the study and after the aims, methods, objectives, and potential hazards of the study have been explained to the patient in language that he/she can understand. The ICF will be signed and dated by the patient and by the investigator or authorized designee who reviewed the ICF with the patient.

Patients who can write but cannot read will have the ICF read to them before signing and dating the ICF.

Patients who can understand but who can neither write nor read will have the ICF read to them in presence of an impartial witness, who will sign and date the ICF to confirm that informed consent was given.

The original ICF will be retained by the investigator as part of the patient's study record, and a copy of the signed ICF will be given to the patient.

If new safety information results in significant changes in the risk/benefit assessment, the ICF will be reviewed and updated appropriately. All study patients will be informed of the new information and provide their written consent if they wish to continue in the study. The original signed revised ICF will be maintained in the patient's study record and a copy will be given to the patient.

7.3 Patient Confidentiality and Data Protection

The investigator will take all appropriate measures to ensure that the anonymity of each study patient will be maintained.

The patient's and investigator's personal data will be treated in compliance with all applicable laws and regulations.

7.4 Institutional Review Board

An appropriately constituted IRB, as described in ICH Guidelines for GCP, will review and approve:

- The protocol, ICF, and any other materials to be provided to the patients (e.g. advertising) before any patient may be enrolled in the study

The [name] Study (V1)

- Any amendment or modification to the study protocol or ICF before implementation, unless the change is necessary to eliminate an immediate hazard to the patients, in which case the IRB will be informed as soon as possible

Ongoing studies will be reviewed by the IRB/EC on an annual basis or at intervals appropriate to the degree of risk.

In addition, the IRB will be informed of any event likely to affect the safety of patients or the continued conduct of the clinical study.

A copy of the IRB approval letter will be sent to Ocular Therapeutix prior to shipment of drug insert supplies to the investigator. The approval letter will include the study title, the documents reviewed, and the date of the review.

Records of the IRB review and approval of all study documents (including approval of ongoing studies) will be kept on file by the investigator.

APPENDICES

I. Itching Score

The physician will ask the patient to grade their current level of itching on a 0 to 4-point scale. The Investigator will record patient graded level of itching on the appropriate Case Report Form.

0 = None

1 = Mild

[figure not shown]
2 = Moderate

3 = Severe

4 = Extremely Severe

II. Palpebral Conjunctivitis Papillae Score

The investigator will grade the level of papillae with the Papillae Efron scale.

III. Conjunctival Injection Score

The investigator will grade the level of ocular injection on a 0 to 4-point scale.

0 = None

1 = Mild – Slightly dilated blood vessels; color of vessels is typically pink; can be quadrantal

[figure not shown]
2 = Moderate – More apparent dilation of blood vessels; vessel color is more intense (redder); involves the majority of the vessel bed

3 = Severe – Numerous and obvious dilated blood vessels; in the absence of chemosis the color is deep red, may be less red or pink in presence of chemosis, is not quadrant

[figure not shown]
4 = Extremely Severe – Large, numerous, dilated blood vessels characterized by unusually severe deep red color, regardless of grade of chemosis, which involves the entire vessel bed

IV. NEI Fluorescein Corneal Staining Scale

Score each of 5 areas of the cornea and total score:

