Investigator-Initiated Trial Study Protocol

Safety and Efficacy of an Intracanalicular Dexamethasone Insert compared to Topical Loteprednol Etabonate Ophthalmic gel 0.38% in Patients with Keratoconus (KC) wearing Rigid Gas Permeable (RGP) Contact Lenses who have been diagnosed with Allergic Conjunctivitis and underlying Dry Eye Disease (DED)

The [name] Study

Compound: DEXTENZA (dexamethasone ophthalmic insert) 0.4 mg, for intracanalicular use

Study Name: The [name] STUDY

Clinical Phase: Open-label, Prospective, Interventional

Date of Issue: February 20, 2020

Primary Investigator: [name], OD
[contact]

Research Coordinator: [name]
Senior Research Coordinator

Site Name & Location: Cornea Center for Clinical Excellence
Illinois College of Optometry
Illinois Eye Institute
[contact]

CLINICAL STUDY PROTOCOL SYNOPSIS

TITLE	Safety and Efficacy of an Intracanalicular Dexamethasone Insert compared to Topical Loteprednol Etabonate Ophthalmic gel 0.38% in Patients with Keratoconus (KC) wearing Rigid Gas Permeable (RGP) Contact Lenses who have been diagnosed with Allergic Conjunctivitis and underlying Dry Eye Disease (DED)- The [name] Study
SITE LOCATION(S)	Cornea Center for Clinical Excellence Illinois College of Optometry Illinois Eye Institute [contact]
PRINCIPAL INVESTIGATOR	[name], OD [contact]
OBJECTIVE(S)	To determine if physician administered intracanalicular dexamethasone insert improve the signs and symptoms of ocular allergy and dry eye disease in KC patients compared to topical loteprednol etabonate ophthalmic gel 0.38%.
STUDY DESIGN	Prospective Open-label Interventional Study
STUDY DURATION	4 months after IRB approval
ESTIMATED STUDY COMPLETION DATE	3 months after DEXTENZA insertion
POPULATION	
Sample Size:	20 patients (40 eyes)
Target Population:	Patients with bilateral keratoconus, wearing RGP contact lenses in both eyes, who have been diagnosed with bilateral allergic conjunctivitis and underlying dry eye disease
TREATMENT(S)	
Study Drug	DEXTENZA (dexamethasone ophthalmic insert) 0.4 mg, for intracanalicular use
Dose/Route/Schedule:	Patients with Keratoconus, with Allergic Conjunctivitis and underlying Dry Eye Disease, wearing RGP contact lenses will have one eye randomized to receive the Sustained Release Dexamethasone, 0.4mg intracanalicular insert (study eye). The fellow-eye will receive topical loteprednol (control eye) on a 4,3,2,1 weekly taper schedule.
ENDPOINT(S)	

Primary:

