2. STUDY OBJECTIVES

2.1 Primary Objective

To determine the effect of dexamethasone intracanalicular insert through Day 90 as measured by:

- Mean change in itching score from Baseline measured at all visits (Visits 1-5)
 - Graded on a scale of 0-4 and determined by asking the patient
- Mean change in palpebral conjunctivitis papillae score from Baseline measured at all visits (Visits 1-5)
 - Graded using the Papillae Efron Scale as graded by the physician
- Mean change in conjunctival injection score from Baseline measured at all visits (Visits 1-5)
 - Graded on a scale of 0-4 as graded by the physician
- Mean change in corneal staining score from Baseline measured at all visits (Visits 1-5)
 - Graded using the NEI Fluorescein Staining Scale as graded by the physician

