3. STUDY DESIGN

3.1 Study Description and Duration

This prospective, open-label, single-center, randomized, fellow-eye, investigator-sponsored clinical study seeks to investigate the safety and efficacy of the dexamethasone insert in the treatment of allergic conjunctivitis and DED signs and symptoms in patients with Keratoconus using RGP contact lenses when compared to topical standard of care loteprednol etabonate ophthalmic gel 0.38%. After screening a given patient for inclusion and exclusion criteria, and gaining informed consent, one eye will be randomized to receive the dexamethasone insert as determined by a coin flip at the screening visit. The remaining eye will be prescribed a loteprednol etabonate ophthalmic gel 0.38% following a 4,3,2,1 weekly taper. Per enrolled eye, the study period will last for approximately 90 days, consisting of five visits. At Screening/ Baseline, Day 0, Day 7, Day 30 and Day 90, primary and secondary endpoints will be assessed alongside standard-of-care procedures. Adjusting for enrollment period, the study will last a total of approximately 3 months. An abstract with preliminary results will be submitted by May 2020 for the AAOpt conference.

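### Itching, the only patient-reported primary endpoint, is asked for and recorded by unmasked study staff, with no requirement to score each eye; a per-eye form completed before the examination would reduce the avoidable part of the risk.

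*Combined protocol and SAP*

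**What the plan says.** Sections 2.1 and the Synopsis list four primary scores. Itching comes from the patient: "Graded on a scale of 0-4 and determined by asking the patient". The other three come from the physician: papillae ("Graded using the Papillae Efron Scale as graded by the physician"), conjunctival injection ("Graded on a scale of 0-4 as graded by the physician") and corneal staining ("Graded using the NEI Fluorescein Staining Scale as graded by the physician").

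Appendix I gives the itching procedure: "The physician will ask the patient to grade their current level of itching on a 0 to 4-point scale", followed by "The Investigator will record patient graded level of itching on the appropriate Case Report Form". The anchors run from 0 (none) to 4 (extremely severe). Appendix I does not mention right and left eye.

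Section 3.1 describes the trial as "This prospective, open-label, single-center, randomized, fellow-eye, investigator-sponsored clinical study". It places the coin flip that allocates the eyes at the screening visit, where Table 1 also schedules an itching score. The order of the two within that visit is not stated. Table 1 schedules the OSDI questionnaire and the itching grade at every visit. No masked assessor, independent interviewer or patient-completed itching form is described.

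**The concern.** In an open-label trial the symptom score is the one primary measure that need not pass through the treating clinician. Appendix I sends it through that clinician anyway. The person asking knows which eye has the insert, and may have placed it. Phrasing, prompting or a patient's wish to please can move an answer on a five-step scale, where one step is a large change.

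The missing eye label is a separate matter. Section 1.2.1 rests the design on comparing two eyes of one patient. If a site recorded a single itching grade per patient, the primary symptom endpoint would say nothing about insert versus gel.

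**Working it through.** No figure in the documents bears directly on this point, so the first three steps compare the text and the fourth is an illustration.

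**1. Who handles each primary score.**

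| Primary score | Source of the grade | Who elicits or grades | Who records |
|---|---|---|---|
| Itching | Patient | Physician asks (Appendix I) | Investigator (Appendix I) |
| Papillae | Physician | Physician (2.1) | Not stated |
| Injection | Physician | Physician (2.1) | Not stated |
| Staining | Physician | Physician (2.1) | Not stated |

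Section 2.1 and the appendices use physician and investigator interchangeably for the graded signs. Whether one person or two handle itching, neither is described as masked.

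**2. Is a score per eye required?** Appendix I asks for the patient's current itching, without naming an eye. Suppose one grade is taken per visit and entered for both eyes. The change from baseline is then identical in the two eyes, so the between-eye difference is 0 in all 20 patients whatever the treatments do. The text does not say that sites will do this. It does not prevent it.

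**3. When is itching scored relative to allocation?** The coin flip is at Visit 1. The Visit 1 itching score may therefore come before or after it. The Day 0 score (Visit 2) necessarily comes after it.

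**4. Illustration of size.** From the documents: 20 pairs. Assumed: a paired t-test at two-sided 5% (the documents name no test), a spurious between-eye difference *b*, a standard deviation of the paired difference *SD*, and no true effect. The false-positive rate is the probability that |T| exceeds 2.093, where T is noncentral t with 19 degrees of freedom and noncentrality *b*√20/*SD*. For *b* = 0.25 and *SD* = 1.0 the noncentrality is 0.25 × 4.472 = 1.118, and the rate is 18.6%.

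| Assumed SD | b = 0.10 | b = 0.25 | b = 0.50 |
|---|---|---|---|
| 0.7 | 9.3% | 32.9% | 85.8% |
| 1.0 | 7.1% | 18.6% | 56.5% |
| 1.3 | 6.2% | 12.9% | 37.2% |

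These rates apply to bias from any source, the patient's own expectation included. What a form gains depends on the share of the bias due to the interviewer, which is unknown. With a total bias of 0.5 and SD 1.0, removing 25%, 50% or 75% of it lowers the rate from 56.5% to 35.7%, 18.6% or 8.3%. It returns to 5% only if all of the bias goes.

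**The case against.** The strongest reply is that the patient is unmasked too. One eye has an insert and the other gets a prescribed gel, so expectation affects the answer whether it is spoken or written. This stands. A reader might infer that a self-completed form would remove the bias, or would make itching an independent check on the physician's signs. The documents support neither, and the protocol does not claim that agreement between symptom and signs is independent confirmation.

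Second, the investigator transcribes a grade that the patient chooses from fixed anchors, and does not judge it. This also stands: the room for influence is narrower than for the three signs. It is not nil, because the question is still put by someone who knows the allocation.

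Third, a reader might infer that bias is present, of known size, or in favour of the insert. The text shows a route for bias and nothing about its occurrence, size or direction.

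Fourth, the OSDI might be taken as proof that a self-completed route already exists. The documents list it as a questionnaire but do not say who completes it or when, so the new form must state this itself.

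Finally, it is tempting to ask also that the signs be graded before the insert is visualized. That would mask nobody, since the physician knows the allocation, and Table 1 and Section 5.2.1 already list visualization after the grading.

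**Conclusion.** The point holds as an avoidable risk in how one primary endpoint is collected, together with a gap in Appendix I on scoring each eye. It does not show that the itching result will be biased. Its size cannot be derived from the documents. The table above rests on assumed bias sizes, SDs and test, and shows only that with 20 pairs even a small systematic shift matters. The change is worth making because it is cheap and bears on a primary endpoint, but the gain is partial. Bias from the patient's own knowledge of treatment remains, and so does the unmasked grading of papillae, injection and staining.

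**What to change.** Reword Appendix I, and bring Section 2.1 and the Synopsis into line:

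- At every visit where itching is scored, the patient marks the 0-4 scale separately for the right and the left eye on a paper form.
- The research coordinator hands out the form before the patient meets the physician and before any examination. At Visit 1 this happens before the coin flip.
- The physician does not see the form until papillae, injection and staining have been entered for that visit.
- For patients who cannot read, whom Section 7.2 already provides for, the coordinator reads the form aloud in neutral terms and marks the answer if the patient cannot.
- The protocol states as a limitation that the patient is unmasked, so itching remains open to expectation bias.

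The cost is one extra page per visit, a little coordinator time, and IRB review of the amended text and the new patient form, which Section 7.4 requires. No additional assessor or visit is needed.
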